6.1.6 Financial Disclosure and Obligations

The investigator is required to provide financial disclosure information to allow the sponsor to submit the complete and accurate certification or disclosure statements required under 45 CFR 46. In addition, the investigator must provide to the sponsor a commitment to update this information promptly if any relevant changes occur during the course of the investigation and for 1 year after the completion of the study.

Neither the sponsor nor the study clinic is financially responsible for further testing or treatment of any medical condition that may be detected during the screening process.

6.2 Confidentiality and Disclosure of Data

All subjects will sign a HIPAA-compliant authorization form containing the mandated core elements and requirements before participation in this clinical study. The sponsor and designees affirm and uphold the principle of the subject's right to protection against invasion of privacy. Throughout this study, a subject's source data will only be linked to the sponsor's electronic data capture system database or documentation via a unique identification number. As permitted by all applicable laws and regulations, limited subject attributes such as gender, age or date of birth, and subject initials may be used to verify the subject and accuracy of the subject's unique identification number.

To comply with ICH Guidelines for GCP and to verify compliance with this protocol, the sponsor requires that the investigator allow review of the subject's original medical records (source data or documents) by the study monitor, representatives from any regulatory authority (e.g., FDA), the sponsor's designated auditors, and the appropriate IRB. These medical records will include, but will not be limited to, clinical laboratory test result reports, ECG reports, admission and discharge summaries for hospital admissions occurring during a subject's study participation, and autopsy reports. Access to a subject's original medical records requires the specific authorization of the subject as part of the informed consent process.

Copies of any subject source documents that are provided to the sponsor must have certain personally identifiable information removed (i.e., subject name, address, and other identifier fields not collected in the subject's eCRF).

Data will be maintained and backed up in the electronic data capture system. All access to the data is protected by username and password, and each staff member and all sponsor staff will have separate access that requires a separate username and password. Access is only given to site staff and requested sponsor staff who have completed the appropriate training.

6.3 Subject Consent

Written informed consent in compliance with 45 CFR 46 will be obtained from each subject before entering the study or performing any unusual or nonroutine procedure that involves risk to the subject. An informed consent template may be provided by the sponsor to the study clinic. If any institution-specific modifications to study-related procedures are proposed or made by the study clinic, the consent should be reviewed by the sponsor or its designee or both before IRB submission. Once reviewed, the consent will be submitted by the investigator to the IRB for review and approval before the start of the study. If the informed consent form is revised during the course of the study, all active participating subjects must sign the revised form.

Before enrollment, each prospective subject will be given a full explanation of the study and be allowed to read the approved informed consent form. The informed consent process will be performed by a clinical research nurse in a private room. The subject will be given unlimited time to ask questions regarding study participation, and each subject will be questioned to ensure their understanding. Once the investigator is assured that the subject understands the implications of participating in the study, the subject will be asked to give consent to participate in the study by signing the informed consent form.

The investigator will provide a copy of the signed informed consent form to the subject. The original form will be maintained in the subject's medical records at the site.

6.4 Data Collection

Full details of procedures for data collection and handling will be documented in the data management plan, which is initiated with the final protocol receipt. The data management plan is a changing document that evolves over the course of the study and is finalized by database lock.

6.5 Publications

No information related to or generated by this study will be released to the public until it has been reviewed by the sponsor. The sponsor shall own intellectual rights for the data and analysis resulting from this study. Authorship on publications will be determined by standard journal requirements.

7. STUDY MANAGEMENT

7.1 Medical Monitor

As outlined in ICH E6(R2) Section 5.3, the sponsor's designated medical monitor will be readily available to advise on trial-related medical questions or problems.

7.2 Study Monitoring

The sponsor or its designee will monitor the study to ensure that it is being conducted according to the protocol, GCP standards, and applicable region-specific requirements, and to ensure that study initiation, conduct, and closure are adequate. The investigators and the study clinic staff will be expected to cooperate fully with the study monitors and personnel or agents of the sponsor and be available during monitoring visits to answer questions sufficiently and to provide any missing information. The investigators and their institutions will permit direct access to source data/documents for study-related monitoring activities, audits, IRB reviews, and regulatory inspections.

During any on-site visits, the study monitor will:

- Check and assess the progress of the study
- Review all informed consent forms
- Review study data collected
- Conduct source document verification
- Identify any issues and address their resolution
- Verify that the facility remains acceptable
- Conduct study drug accountability

These monitoring activities will be done in order to verify that the:

- Data are authentic, accurate, and complete.
- The safety and rights of the subjects are being protected.
- The study is being conducted in accordance with the currently approved protocol (including any amendments), GCP, and all applicable regulatory requirements.

In addition, the sponsor, designated auditors, and government inspectors must be allowed access to eCRFs, source documents, and other study files that may be required to evaluate the conduct of the study.

7.3 Management of Protocol Amendments and Deviations

7.3.1 Modification of the Protocol

Any changes in this research activity, except those necessary to remove an apparent immediate hazard to the subject, must be submitted to the sponsor or designee and reviewed and approved by the local IRB before implementation. Amendments to the protocol must be submitted in writing to the investigator's IRB for approval before subjects are enrolled into an amended protocol.

7.3.2 Protocol Violations and Deviations

Any significant protocol deviations that the investigator or study clinic staff believes are of major importance (e.g., incorrect randomizations, subject enrolled but not eligible) should be reported to the sponsor and the investigator's IRB as soon as possible. Significant protocol deviations may include the following:

- Deviations from the inclusion/exclusion criteria that may affect subject safety
- Deviations (omission or delay) of safety monitoring procedures
- Deviations in the administration of the study drug
- Deviations in obtaining informed consent

All subjects who are enrolled and receive the study drug, regardless of whether they have a major protocol violation, must continue to be followed for safety for all follow-up study visits.

9. APPENDICES

9.1 Appendix A – Schedule of Events

Table 9-1: Schedule of Events

Pharmacokinetics of Multiple Repeated Doses of Intranasal Naloxone										
	Screening	Check-In and Baseline	Treatment Period							Check-out
Study Day	-28 to -2	-1	1	2	3	4	5	6	7	8
Hour										
Visit	1	2	2	2	2	2	2	2	2	2
Recruitment/Screening - healthy	X									
Screening Failures	X									
In House Residency		X	X	X	X	X	X	X	X	
Meals		X	X	X	X	X	X	X	X	
Informed Consent	X									
Medical History	X	X								
Comprehensive Physical Exam	X	X								X
Vital signs ¹	X	X	X	X	X	X	X	X	X	X
Height	X									
Weight	X	X								X
ECG - single ²	1	1	3			3			3	1
Chemistry/hematology ³	X	X								X
Urinalysis	X	X								X
Urine drug screen + alcohol screen	X	X								X
Pregnancy test ³ (females only)	X	X								X
FSH (females only)	X									
HIV test	X									
Hepatitis test	X									
SARS CoV-2 Molecular Test		X								
Study Agent preparation & administration - IN			X			X			X	
Plasma PK draw (See protocol for time points)			16			16			16	
Nasal Irritation Assessment (See protocol for time points)			6			6			6	
Con Med/AE Assessment	X	X	X	X	X	X	X	X	X	X
eSource Management		X								
			Dosing Day	Wash-out Day	Wash-out Day	Dosing Day	Wash-out Day	Wash-out Day	Dosing Day	

1 Vital signs will be taken at 0 (pre-dose), 0.5h, 1h and 6h timepoints on dosing days

2 Clinically notable results are repeated; ECG will be performed at 0 (pre-dose), 1h and 6h timepoints on dosing days

3 Serum test

9.2 Appendix B – List of Abbreviations

LIST OF ABBREVIATIONS

Abbreviation	Definition
AE	adverse event
AUC _{0-inf}	area under the concentration-time curve from 0 to infinity
AUC _{0-t}	area under the concentration-time curve from 0 to last quantifiable concentration
CFR	Code of Federal Regulations
C _{max}	maximum observed concentration
COVID-19	coronavirus disease of 2019
CDER	Center for Drug Evaluation and Research
DARS	Division of Applied Regulatory Science
ECG	Electrocardiogram
eCRF	electronic case report form
FDA	Food and Drug Administration
GCP	Good Clinical Practice
HBsAg	hepatitis B surface antigen
HepC	hepatitis C
HIPAA	Health Insurance Portability and Accountability Act
HIV	human immunodeficiency virus
ICH	International Council for Harmonisation
IRB	Institutional Review Board
IN	Intranasal
Kg	kilogram
MAP	modeling analysis plan
MedDRA	Medical Dictionary for Regulatory Activities
Mg	milligram
NSAID	nonsteroidal anti-inflammatory drug
pAUC	partial area under the curve
PD	Pharmacodynamic
PK	Pharmacokinetic
SAE	serious adverse event
SAP	statistical analysis plan
SARS-CoV-2	severe acute respiratory syndrome coronavirus 2
SD	standard deviation
t _{1/2}	terminal half-life
TEAE	treatment-emergent adverse event
t _{max}	time of C _{max}

9.3 Appendix C – Protocol Revision History

PROTOCOL REVISION HISTORY			
Protocol Number	Version	Effective Date	Summary of Changes
SCR-011	1.0	15 Feb 2021	Developed initial protocol

 9.1 Randomization schedule17

10. References.....18

Abbreviations and definitions

AE	Adverse event
AUC _{0-inf}	Area under the plasma concentration time curve from time 0 extrapolated to infinity
AUC _{0-t}	Area under the concentration-time curve from 0 to last quantifiable concentration
C _{last}	Last quantifiable concentration
C _{max}	Maximum observed plasma concentration
CV	Coefficient of variation
ECG	Electrocardiogram
eCFRs	Electronic case report forms
FDA	Food and Drug Administration
IN	Intranasal
inf	Infinity
K _{el}	Elimination rate constant
pAUC	partial area under the curve
PD	Pharmacodynamic
PK	Pharmacokinetic
SAP	Statistical analysis plan
SD	Standard deviation
t _{1/2}	Terminal half-life
TEAE	Treatment-emergent adverse event
T _{max}	Time of maximum concentration (C _{max})

Change Log

Version / Date	Section	Summary of Changes
1.0 / 10 Mar 2021	General	Developed initial statistical analysis plan

1. Introduction

This document outlines the proposed statistical methods for data analysis of data collected from Protocol ‘SCR-011: Clinical study to investigate the pharmacokinetics of multiple repeated doses of intranasal naloxone’.

The following statistical analysis plan (SAP) provides the framework for the summarization of the data from this study. The SAP may change due to unforeseen circumstances. Any changes made to the SAP will be documented in a change log within the SAP along with a rationale for the changes.

2. Study Objectives

The study objectives are:

1. To determine and compare the pharmacokinetics of intranasal (IN) naloxone between the 4-dose naloxone arms and the 2-dose naloxone arm.
2. To use the pharmacokinetic data from each of the 3 naloxone dosing schedules/doses to predict the time to reverse opioid-induced respiratory depression following different overdose scenarios based on pharmacokinetic/pharmacodynamic (PK/PD) models

3. Study Overview

3.1 Study Design

This study will be a randomized, unblinded, three-way crossover study to determine naloxone plasma concentration after administration of multiple doses of intranasal (IN) naloxone.

Table 3-1: Study Schedule

Day -1	Day 1	Days 2-3	Day 4	Days 5-6	Day 7	Day 8
Check-in	Treatment Period 1	Washout	Treatment Period 2	Washout	Treatment Period 3	Check-out

The following 3 treatments will be evaluated in a randomized order over the 3 treatment periods.

Table 3-2: Study Treatments

Treatment	Description
A	Four 4 mg IN naloxone doses (1 dose every 2.5 min; L at 0 min, R at 2.5 min, L at 5 min, R at 7.5 min)
B	Four 4 mg IN naloxone doses (2 doses every 2.5 min; L and R at 0* min, L and R at 2.5* min)
C	Two 4 mg IN naloxone doses (L at 0 min, R at 2.5 min)

*L = Left Nostril, R = Right Nostril, * doses will be ~5 seconds apart (one after the other)*

Healthy subjects will be randomized to one of six treatment sequences (i.e., ABC, ACB, BAC, BCA, CAB, CBA). FDA will prepare the randomization schedule. Subjects will report to the study site for screening from Days -28 to -2 and then will return to the site on Day -1 for baseline assessments and check-in. After check-in (Day -1), subjects will receive dosing for the 3 respective treatment periods on Days 1, 4 and 7. There will be two days of washout between each treatment period. Participants will be confined in the study clinic from Day -1 until the morning of Day 8. On dosing days, dosing will occur as per the treatment description and PK assessments will occur at the following time points:

- PK assessment: 0 (pre-dose), 2, 4.5, 7, 10, 12.5, 15, 20, 30, 45, 60, 120, 180, 240, 360, and 720 minutes

The subject should remain fully supine for approximately one-hour post-dose. Subjects should be instructed not to breathe through the nose during administration of the nasal spray into the nose. Subjects will be instructed to leave their masks off for twenty minutes after drug administration.

A summary of all assessments prior to and following study drug administration on Day 1, is described in the Protocol, Schedule of Events.

Subjects will be discharged from the study after completion of all study procedures. If a subject discontinues from the study prematurely, all procedures scheduled for the end of the study will be performed.

4. Study Endpoints

4.1 Primary Endpoint

First time point when there is a higher naloxone plasma concentration in the 4-dose naloxone arms compared to the 2-dose naloxone arm

4.2 Secondary Endpoints

1. First time point when there is a higher naloxone plasma concentration in the 4-dose naloxone arm B (2 doses every 2.5 minutes) compared to the 4-dose naloxone arm A (1 dose every 2.5 minutes)
2. Dose-proportionality of the 4-dose naloxone arms in reference to the 2 -dose naloxone arm based on C_{max} , AUC_{0-inf} and AUC_{0-t}
3. Predicted time to rescue a patient from simulated opioid-induced respiratory depression from fentanyl and carfentanil following medium and high overdose scenarios

4.3 Exploratory Endpoint

Naloxone C_{max} , AUC_{0-inf} , AUC_{0-t} , t_{max} , and partial AUC [pAUC] within the first 30 minutes of dosing

4.4 Sample Size

Twenty healthy participants are planned for enrollment with up to 4 replacements. Naloxone plasma concentration profiles and variabilities were calculated based on summary pharmacokinetic data from the IN naloxone product label. Predicted naloxone concentrations were determined for each of the proposed dosing treatments based on principles of superposition (i.e., for linear pharmacokinetics the total concentration of a drug in circulation is the sum of remaining concentration from each administered dose prior to the current measurement time) with a focus on comparing plasma concentrations at early timepoints. Power calculations were based on the ratio between concentrations for each of the two primary comparisons (Treatment A vs Treatment C and Treatment B vs Treatment C). Of the comparisons, the power for the 4-dose naloxone arm A (test) versus the 2-dose naloxone arm C (reference) was expected to be lower than the 4-dose naloxone arm B (test) versus the 2-dose naloxone arm C (reference). For the different proposed treatments, the ratio in concentrations and the coefficient of variation (CV) at each timepoint based on principles of superposition are shown in Table 4-1.

Table 4-1: Predicted concentration ratio and CV between treatments at different timepoints and power calculation at a 0.0221 significance level

Comparison	Time (min)	Concentration Ratio	CV	Power (n=18) at $p = 0.0221$
Primary Endpoint (comparisons of 4-dose treatment arms vs. 2-dose treatment arm reference)				
Treatment A vs Treatment C	10	1.36	68	49
	12.5	1.57	58	91
	15	1.78	48	100
Treatment B vs Treatment C	4.5	2	111	86
	7	2	90	94
	10	2	68	99
Secondary Endpoint (comparison between the 4-dose treatment arms)				
Treatment B vs Treatment A	4.5	2	111	86
	7	1.85	90	88
	10	1.47	68	68

As the intent of administering naloxone is rapid reversal of an overdose, the planned primary analysis is a comparison of naloxone concentrations between treatment arms across pre-specified consecutive time points. Each of the paired comparisons was assumed to include three pre-specified timepoints (timepoints correspond to those listed in Table 4-1). The time points will be evaluated sequentially with adjustments for multiplicity using Pocock boundaries (Pocock, 1977). For three pre-specified assessments, this would correspond to assessments at a 0.0221 significance level for comparisons at individual time points to maintain an overall 0.05 significance level.

Based on these considerations and the concentration ratios and CVs in Table 4-1, a sample size was determined so that at least one of the planned time points would have greater than 90% power at a 0.0221 significance level for a one sided, log-transformed paired comparison (for the primary endpoint). For concluding an increase in naloxone concentration for Treatment A compared to Treatment C at 15 minutes, at least 12 subjects would be necessary assuming a 1.78-fold increase in exposure and 48% CV for the treatments. For concluding an increase in naloxone concentration for Treatment B compared to Treatment C at 10 minutes, at least 12 subjects would have the desired power assuming a 2-fold increase in exposure and 68% CV for the treatments. The sample size was further increased to 20 subjects to account for discontinuations and situations where the CV values in Table 4-1 may be underestimated for repeat naloxone dosing.

5. Analysis Populations

The PK population will include all subjects who receive study drug and have at least one estimable PK parameter after dosing. The safety population will include all subjects who receive

at least 1 dose of the study drug. The analysis population will include all subjects in the PK population with sufficient data to calculate PK parameters. Only subjects with results from two or more periods will be included in comparisons. Treatment in all analysis populations will be assigned based upon the treatment which the subjects actually received.

6. Data Screening and Acceptance

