4.9.1 Analysis Populations

The PK population will include all subjects who receive study drug and have at least one estimable PK parameter after dosing.

The safety population will include all subjects who receive at least one dose of the study drug.

The analysis population will include all subjects in the PK population with sufficient data to calculate PK parameters. Only subjects with results from two or more periods will be included in comparisons.

The details of the PK analysis will be included in the Statistical Analysis Plan (SAP). In any situation where the SAP and protocol differ regarding planned analyses, the language in the SAP supercedes descriptive text in the protocol.

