4.9.5 Pharmacokinetic Analysis

Pharmacokinetics: Concentrations will be determined at specified times. The primary endpoint is the first timepoint when there is a higher naloxone plasma concentration in the 4 naloxone dose arms compared to the 2 naloxone dose arm. The comparisons will consider multiple, pre-specified timepoints and adjust for multiplicity using Pocock boundaries. Separate comparisons will be performed looking at the 4 naloxone dose arm A (test) versus the 2 naloxone dose arm C (reference) and the 4 naloxone dose arm B (test) versus the 2 naloxone dose arm C (reference). Different timepoints will be selected for each comparison and timepoints will be evaluated from earliest to latest time.

Secondary endpoints will include determination of the first timepoint when there is a higher naloxone plasma concentration in the 4 naloxone dose arm B (2 doses every 2.5 minutes) as test compared to the 4 naloxone dose arm A (1 dose every 2.5 minutes) as reference. The same approach as outlined for the primary endpoint analysis above will be used for this comparison.

Additional PK measures (i.e., C_{max} , AUC_{0-inf} , AUC_{0-t} , pAUC, T_{max} , half-life, elimination rate) will be exploratory endpoints and determined for each subject using non-compartmental

methods. All parameters will be calculated using SAS or R software and will be reported with standard descriptive statistics including the mean and coefficient of variation. Calculation of PK parameters will be performed using actual sampling times. Additional details of the PK analysis will be included in the SAP.

Dose Proportionality: Dose proportionality based on C_{max} , AUC_{0-t} , and AUC_{0-inf} will be compared between each of the three naloxone treatments as secondary endpoints. The 4 naloxone doses arms (separate comparisons for 1 dose every 2.5 minutes and 2 doses every 2.5 minutes) will be compared with the 2 naloxone dose arm (1 dose every 2.5 minutes). An additional comparison will be performed between the 4 naloxone arm B (2 doses every 2.5 minutes) as test and 4 naloxone dose arm A (1 dose every 2.5 minutes) as reference.

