6.1 Handling of Missing and Incomplete Data

The following approaches will be used for the handling of missing and incomplete data:

- Missing PK data (e.g., skipped plasma sample collected) will not be imputed.
- Missed dose, dose administered outside the window, or other issues with dose administration (e.g., product delivery fails) will result in PK data from that period for that subject being excluded from all treatment arm comparisons and summary statistics from that time point forward. Other situations, such as a subject sneezing in close proximity to dosing will be carefully documented by study staff and handling of these cases will be determined and documented before any concentration data is available.
- PK samples collected outside the protocol-defined sampling window (i.e., more than \pm 0.5 minute from the scheduled time for the first 15 minutes of collections) will be excluded from analyses comparing naloxone concentrations at the specific time point that is outside the window.
- PK measurements below the lower limit of quantification will be set to zero for all analyses.

7. General Statistical Considerations

All data will be presented in data listings. Data from subjects excluded from an analysis population will be presented in the data listings, but not included in the calculation of summary statistics. Demographic and baseline characteristics will be summarized overall and by treatment for all subjects.

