7.3 Pharmacokinetic Analyses

7.3.1 Naloxone Concentration Comparisons

The primary endpoint is the first timepoint when there is a higher naloxone plasma concentration in the 4-dose naloxone arms compared to the 2-dose naloxone arm. Separate comparisons will be performed with the 4-dose naloxone arm A (test) versus the 2-dose naloxone arm C (reference) and the 4-dose naloxone arm B (test) versus the 2-dose naloxone arm C (reference). No adjustment for multiplicity is planned for these separate comparisons.

Secondary endpoints will include determination of the first time point when there is a higher naloxone plasma concentration in the 4-dose naloxone arm B (2 doses every 2.5 minutes) as test compared to the 4-dose naloxone arm A (1 dose every 2.5 minutes) as reference. The same approach outlined for the primary endpoint analysis above will be used for this secondary endpoint comparison. The secondary endpoint analysis will be conducted regardless of the primary endpoint results.

Table 7-1: Pre-specified Timepoints and p -value Threshold for Comparing Naloxone Concentrations Across Treatments (Maintain Overall p -value Per Comparison at 0.05) (Pocock, 1977)

Comparison	Time (min)	Interim Analysis	p -value Threshold
Treatment A vs Treatment C (primary)	10	1	0.0221
	12.5	2	0.0221
	15	3 (final)	0.0221
Treatment B vs Treatment C (primary)	4.5	1	0.0221
	7	2	0.0221
	10	3 (final)	0.0221
Treatment B vs Treatment A (secondary)	4.5	1	0.0221
	7	2	0.0221
	10	3 (final)	0.0221

For both the primary and secondary analyses, up to three different time points have been pre-specified for each comparison. Time points will be evaluated from earliest to latest time (Table 7-1). Testing will be conducted sequentially along planned interim analyses (i.e., start at the initial time and progress forward, stopping if success is achieved) at a 0.0221 significance level. Testing will proceed through each time point until either one passes (reported as the earliest time where a difference in concentration is observed) or all pre-specified time points fail (no difference in naloxone concentrations between treatments for the selected time points).

For comparing treatment A to treatment C, the analysis will use naloxone concentration data collected at 10, 12.5, and 15 min. For both the treatment B to treatment C comparison and the treatment B to treatment A comparison, the pre-specified time points are 4.5, 7, and 10 min. All

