subjects contributing naloxone concentration measures from both treatments at the pre-specified time points will be included in the analysis. At each of these timepoints, subject-level naloxone concentration will be log-transformed. Naloxone concentration values that are below the lower limit of quantification (i.e., zero) will result in that time point from that subject being removed for comparisons involving that treatment arm.

A paired Student's t-test will be used for comparing naloxone concentrations between treatments. To demonstrate an increase in naloxone concentration with the test compared to reference, it is necessary that the lower bound of the one-sided 97.79% interval for the geometric mean ratio excludes 1. The results will be transformed back to the original scale by exponentiation to provide treatment geometric means.

Normality assumption will be verified using the Shapiro-Wilke test for normality and homogeneity of variances will be verified using Levene's test. If either assumption is not valid, a Mann-Whitney-U test will be used for the comparisons rather than a t-test.

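### Testing three sampling times at 0.0221 each does not by itself secure an overall 0.05: Pocock's constant is for accumulating data, and the correlation that sets the level here is not given

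*SAP*

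**What the plan says.** SAP 4.4 (Sample Size) fixes three sampling times for each comparison and adjusts for testing all three with Pocock boundaries, stating that "this would correspond to assessments at a 0.0221 significance level for comparisons at individual time points to maintain an overall 0.05 significance level". The caption of Table 7-1 in SAP 7.3.1 repeats the claim: "Maintain Overall p -value Per Comparison at 0.05".

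The times are 10, 12.5 and 15 min for A versus C, and 4.5, 7 and 10 min for B versus C and for B versus A. Table 7-1 numbers them as interim analyses 1, 2 and 3 (final), and the text says "Testing will be conducted sequentially along planned interim analyses", from earliest to latest, stopping at the first success.

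The tests are one-sided. The sample size is set "for a one sided, log-transformed paired comparison", and in the analysis "it is necessary that the lower bound of the one-sided 97.79% interval for the geometric mean ratio excludes 1". Protocol 4.9.5 says the same in general terms: "The comparisons will consider multiple, pre-specified timepoints and adjust for multiplicity using Pocock boundaries".

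The subjects tested can differ from one time to the next. Under SAP 6.1, a sample taken outside its window "will be excluded from analyses comparing naloxone concentrations at the specific time point that is outside the window", and SAP 7.3.1 removes values below the quantification limit at the affected time.

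**The concern.** Pocock's constant holds a 5% level because the correlations between looks are known in advance. Each look contains all the data of the look before, so with equal spacing the correlation between looks i and j is √(i/j). In this trial the three tests use three different measurements taken in the same dosing periods and analysed after collection. Their correlation is a property of naloxone absorption and assay noise, not of the design. Table 4-1 gives a CV for each time but nothing that links the times.

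At stake is the stated 0.05 error rate for the primary endpoint. As written, it rests on a method whose conditions the design does not meet.

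**Working it through.** **Inputs.** Per-time level 0.0221, three times, overall 0.05 (SAP 4.4, Table 7-1); one-sided paired t-test on log concentrations (SAP 4.4, 7.3.1); n = 18, ratios and CVs from Table 4-1. The between-time correlation r is an assumption and is varied from 0 to 0.9.

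**1. Where 0.0221 comes from.** With the accumulating-data correlations √(1/2) = 0.707, √(1/3) = 0.577 and √(2/3) = 0.816, the constant boundary with overall two-sided level 0.05 is 2.289, a nominal p of 0.02205. This matches the SAP figure. The one-sided constant would be 0.0232. Under these correlations, 0.0221 gives 5.01% two-sided and 4.78% one-sided, so one-sided use is not itself the problem.

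**2. The sidedness is confirmed by the power table.** Taking the SD of the log difference as √ln(1 + CV²) and noncentral-t power at n = 18, one-sided 0.0221 reproduces all nine entries of Table 4-1 within rounding. For A versus C at 10 min it gives 49.1% against the stated 49; a two-sided test would give 36.9%.

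**3. Level of the planned procedure when no time differs.** The level is P(at least one of three statistics exceeds its one-sided 0.0221 critical value).

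| r | Equal correlations | AR(1), r between adjacent times | Simulated paired t, n = 18, equal correlations |
|---|---|---|---|
| 0 | 6.48% | 6.48% | 6.46% |
| 0.3 | 6.08% | 6.18% | 6.16% |
| 0.5 | 5.59% | 5.77% | 5.69% |
| 0.7 | 4.87% | 5.09% | 5.01% |
| 0.9 | 3.73% | 3.91% | 3.82% |

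The r = 0 entry is 1 − (1 − 0.0221)³ = 6.48%. The first two columns use normal theory; the simulation used 400,000 trials per value. The level crosses 5% at r = 0.67 (equal) or 0.72 (AR(1)). The ceiling for any correlation is 3 × 0.0221 = 6.63%, and at r = 1 the level is 2.21%.

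**4. Level when one time truly differs.** At most two null times remain. The ceiling is 2 × 0.0221 = 4.42%. At r = 0 it is 1 − (1 − 0.0221)² = 4.37%, and at r = 0.9 it is 3.13%.

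**5. A threshold that needs no correlation.** Bonferroni gives 0.05/3 = 0.0167. With no true difference the level is 4.9% at r = 0 and 2.9% at r = 0.9.

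| Comparison (times in min) | Power at 0.0221 | Power at 0.0167 |
|---|---|---|
| A vs C (10, 12.5, 15) | 49.1 / 90.7 / 99.9% | 43.9 / 88.2 / 99.8% |
| B vs C (4.5, 7, 10) | 85.8 / 94.2 / 99.3% | 82.4 / 92.3 / 99.0% |
| B vs A (4.5, 7, 10) | 85.8 / 87.9 / 68.4% | 82.4 / 84.8 / 63.5% |

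At the 12 subjects named in SAP 4.4, power at 0.0167 is 96.3% for A versus C at 15 min and 91.1% for B versus C at 10 min.

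**The case against.** The strongest reply is that the harm is small and may be absent. Samples 2.5 to 3 minutes apart, from the same subject and the same two dosing periods, may well give highly correlated differences. Above roughly 0.7 the plan is at or below 5%, and the worst possible excess is 6.63 − 5 = 1.63 points. That excess also requires no difference at any of the three times, although Table 4-1 predicts ratios of 1.36 to 2 at all nine tests. The endpoint is the first time at which a difference appears, so the most natural error is naming a time too early when a later one is real. That error is held to 4.42% at any correlation. All of this stands. It limits the consequence, but it does not supply the missing basis for the 0.05 claim, because the plan neither states nor bounds the correlation.

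A second reply is that Bonferroni gives up power needlessly. Holm's procedure also holds at any correlation and, in simulation under Table 4-1, raises power to claim the earliest time to 64–65% for A versus C and 92–93% for B versus C. This is true. However, Holm tests in order of p-value rather than of time, and it has no simple confidence bound to match the decision rule in SAP 7.3.1. It is a legitimate choice if the sponsor accepts both changes; it does not make Bonferroni unsound.

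**Conclusion.** The concern holds. The SAP attributes to its procedure an overall 0.05 level that the cited method does not deliver for this design. When no time differs, the level lies between about 2.2% and 6.6% depending on an unstated correlation, and it exceeds 5% only below about 0.67 to 0.72. Actual inflation is not shown. With at least one real difference, the false-claim rate stays at or below 4.42%.

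These figures assume that each single test holds its own 0.0221 level. They concern one comparison at a time; the choice not to adjust across A versus C and B versus C, and the nonparametric fallback test, are separate matters. The point should be corrected because it concerns the error rate of the primary endpoint and the correction costs little.

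**What to change.** In SAP 4.4, 7.3.1 and Table 7-1:

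- Keep testing from earliest to latest time.
- Replace 0.0221 with one-sided 0.05/3 (0.0167), and the 97.79% lower bound with a 98.33% bound.
- State that the overall 0.05 is one-sided and applies to each comparison separately.
- Drop the interim-analysis labels and the reliance on Pocock.
- Restate the power column of Table 4-1.

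This holds at any correlation and with different subjects at different times, provided each single test holds its level.

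**Cost.** Sample size and conduct do not change. Each primary comparison keeps at least one time above 90% power, at n = 18 and at n = 12. The chance of success at some time stays at 99.8–100% for A versus C and 99.0–100% for B versus C; for B versus A it goes from 91–99% to 88–99%. The main loss is at the earliest time: 49.1 − 43.9 = 5.2 points for A versus C, and 85.8 − 82.4 = 3.4 points for the other two comparisons. Some trials will therefore report a later first time.

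**Alternative.** A within-subject sign-flip max-T test uses the observed correlation. Its simulated error is 5.1, 4.9 and 5.2% at r = 0, 0.5 and 0.9 (simulation standard error 0.15 points), and its power at the earliest time is 44–55% for A versus C and 83–89% for B versus C. It is suitable only if the SAP also gives the matching confidence bound and a rule for subjects missing at single times.

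The Protocol names Pocock boundaries in the Synopsis, 4.9.1 (Sample Size) and 4.9.5. Its 4.9.1 (Analysis Populations) already provides that, where planned analyses differ, "the language in the SAP supercedes descriptive text in the protocol"; the difference should be recorded in the SAP change log with its reason.
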